FAQ	Pfeffer Functional Activities Questionnaire
GLMM	General linear mixed model
HR	Hazard Ratios
IADL	Instrumental Activities of Daily Living
IQ-CODE	Informant Questionnaire on Cognitive Decline in the Elderly
LPS 50+	Leistungsprüfsystem für 50- bis 90-Jährige
MMSE	Mini Mental State Examination
MoCA	Montreal Cognitive Assessment
PD	Parkinson's Disease
PD-ABB-Scale	PD Angehörigen Belastungs- und Befindlichkeitsskala
PDD	Parkinson's Disease Dementia
PD-CN	Parkinson's Disease with Normal Cognition
PD-MCI	Parkinson's Disease with Mild Cognitive Impairment
RBD	REM (Rapid Eye Movement) Behavior Disorder
UKT	Universitätsklinikum Tübingen
UPDRS-III	Unified Parkinson's Disease Rating Scale Part III (Motor Part)
ROC	Receiver Operating Characteristic
SWE	Skala zur Allgemeinen Selbstwirksamkeitserwartung
WIE	Wechsler Intelligenztest für Erwachsene
ZCBI	Zarit Caregiver Burden Inventory

3. Study summary

3.1. Background

Presence and severity of non-motor symptoms modulates the rate of Parkinson's Disease (PD) progression with a high impact on patients' quality of life [1-3]. One major clinical milestone in the course of the disease is the conversion to Parkinson's disease dementia (PDD), dramatically increasing the risk for nursing home placement and mortality [4]. Patients with PD have an almost 6-fold increased risk of developing cognitive impairment and PDD compared to age-matched controls [5]. Identification of a high-risk group for converting to PDD (i.e., those PD patients who are in the prodromal dementia phase) is essential to develop and implement early and effective treatments for preventing or delaying dementia. Mild cognitive impairment (PD-MCI) is one of the greatest risk factors for future PDD [6]. A recent meta-analysis found that, on average, 31% of patients with PD-MCI converted to PDD within seven years; however, 24% of patients with PD-MCI reverted back to normal cognitive function [7]. Consequently, the false positive rate for predicting PDD among patients with PD-MCI is high, and better predictive markers to define patients at high risk for PDD development are urgently needed. Therefore, a combination of different markers, including clinical, genetic, and other biomarker data, are proposed to increase ability to predict cognitive worsening and dementia [8-11].

Significant impairments in activities of daily living (ADL) function, in addition to impaired cognition, are the core criterion for diagnosing Parkinson's Disease dementia [12]. Recent studies have shown that even patients with mild cognitive impairment display first signs of ADL dysfunction [13-15], possibly indicating a group at risk for dementia [16]. As the diagnosis of ADL deficits requires these to be solely caused by cognitive deficits, an important step for accurate diagnoses is the measurement of ADL deficits in PD. To confirm the diagnosis of PDD, ADL disabilities should be primarily caused by cognitive, not motor, dysfunction [17, 18]. As PD is primarily a movement disorder, the distinction between motor and non-motor contributions to ADL in PD is an obvious challenge [13]. ADL can be divided into basic (e.g., self-maintenance skills) and instrumental functions (e.g., complex skills). Of these, instrumental ADL (IADL) function is impaired in the earlier stages whereas basic ADL can be preserved for a long time [19]. Based on data of the first follow-up in our non-demented sample (ethic protocol: Baseline 686/2013BO1; Follow-up 284/2018BO1, see below 3.2 *Preliminary data*), we were able to show that the presence of both mild cognitive IADL impairment and PD-MCI dramatically increases the risk for PDD: nearly 50% with baseline profile of both markers converted to dementia within three years. In general, our results argue for the importance of differentiating between cognitive and motor aspects of ADL function in PD. Patients with PD-MCI and cognitive IADL impairment may be a valuable target group for clinical trials aiming to slow down development of dementia. However, this assumption needs to be confirmed by future longitudinal data.

In PD, it is unclear whether self- or informant-reports are more useful for judging ADL impairments in the clinical routine, as the loss of functional independence is an important outcome of disease progression. Although IADL is commonly assessed by an informant who can reliably give information regarding patients' level of functioning, cognitive IADL data was collected from both patients and informants in our study. While discrepancies between self- and informant-ratings are greatest in PDD patients [20], between-group comparisons on IADL item, total, and subscore levels did not show differences between raters. However, it is known

that self-reports on the impact of cognitive changes on IADL function are more sensitive in early stages of cognitive decline [21]. Recently, analysis in this cohort showed that agreement between patient- and informant-ratings of IADL function using Pfeffer Functional Activities Questionnaire (FAQ) items were moderate, with only few items reaching substantial agreement [22]. Ratings of patients and informants were associated with patients' cognitive status, but also other characteristics. Therefore, it is currently unclear whether ratings of patients and/or caregiver have a higher prognostic ability to predict decline in cognition and everyday function. We therefore propose a second follow-up of an already existing large PD cohort to longitudinally investigate the association between IADL function rated by either patients themselves or caregivers, cognition, and other clinical and biomarker measures.

3.2. Preliminary data

Methods. The study was conducted as the first follow-up (Title: Cognitive driven ADL impairment as a predictor for PDD; ethic protocol: 284/2018BO1) of "Amyloid-Beta in Cerebrospinal Fluid as a Risk Factor for Cognitive Dysfunction in Parkinson's Disease" (ABC-PD) study (ethic protocol: 686/2013BO1).

The FAQ quotient (cut-off >1), indicating more cognitive than motor-driven IADL impairment, defined cognitive IADL impairment status at baseline ($FAQ_{Q>1}$). The FAQ is a ten item IADL assessment scored on a 4-point Likert scale ranging from normal (score=0) to dependent (score=3) ADL function (max. points 30) [23]. The FAQ quotient was developed by differentiating cognitive and motor aspects of the individual items. Ten linear regressions were conducted defining each FAQ item as the dependent variable, and the Unified Parkinson's Disease Rating Scale Part III (UPDRS-III, motor assessment) as well as the Montreal Cognitive Assessment (MoCA) total score as independent variables, with age, sex, and disease duration entered as covariates [24]. Hazards ratios (HR) were used to compare the impact of different baseline classifications on dementia conversion.

Results. Of 268 patients with PD assessed at baseline, 108 (40.3%) had PD-MCI. After a period of 3.8 ± 0.8 years, 182 (61.2%) patients were re-assessed and 164 analysed (17 excluded due to deep brain stimulation, one patients without classification of cognitive group). At follow-up, 93 (56.7%) patients fulfilled criteria for normal cognitive function (PD-CN), 54 for PD-MCI (32.9%), and 17 (10.4%) had developed dementia. Predictive ratio of baseline cognitive IADL impairment (n=37; 21.3%) for dementia conversion was descriptively higher than for PD-MCI, but highest in patients with both markers [HR=12.01, 95%-confidence interval (CI): 4.47-32.23]. Nearly half of patients (n=10, 47.6%) with baseline classification of cognitive IADL impairment and PD-MCI converted to dementia. Baseline status of cognitive IADL impairment was associated with higher non-motor burden, worse cognitive performance, and more severe IADL progression over the study period. In a post-hoc Receiver Operating Characteristic (ROC) analysis, the FAQ quotient (cut-off >1.008) was confirmed to best predict conversion to dementia compared to other IADL scores. Only two patients with baseline status of cognitive IADL impairment in our sample scored below the newly identified FAQ quotient cut-off of 1.008 resulting in a total of 35 (21.3%) patients with values above this defined cut-off. The FAQ motor score [AUC(area under the curve)=0.60, 95%-CI: 0.52-0.67, $p=0.13$], reflecting predominantly motor aspects on IADL function, was not associated with PDD conversion.

4. Objectives of the study

Based on previous analyses in the sample we suggest that monitoring of both cognition and cognitive ADL impairment reflect neurodegeneration associated to PDD development. This study evaluates markers predicting cognitive and ADL long-term outcome in our sample. Additionally, we will investigate whether ratings of patients or informants best predicted decline of cognitive impairment and/or everyday function. Clinical data along with other clinical marker and biomarker status will be investigated.

4.1. Hypothesis and research questions

Based on previous reports and preliminary results, we hypothesize that PD-MCI patients with a more pronounced cognitive-driven ADL impairment ($FAQ_{Q>1.008}$) are at higher risk for worsening in cognition and conversion to PDD than PD-MCI patients with ADL impairment primarily related to motor function ($FAQ_{Q\leq 1.008}$).

1. *Prediction of cognitive progression along with progression in IADL function over time*

- Aim 1.1: Prediction of conversion rates to PD-MCI (among PD-CN) and PDD (among non-demented patients) according to baseline IADL, cognitive, genetic, and biomarker profiles in blood and CSF
- Aim 1.2: Prediction of progression in cognitive scales according to cognitive, IADL, genetic, and biomarker profiles in blood and CSF
- Aim 1.3: Prediction of worsening in available ADL scales (patient-/informant-ratings) according to cognitive, IADL, genetic, and biomarker profiles in blood and CSF

2. *Defining the interaction of progression in markers over time*

- Aim 2.1: Evaluation of progression in varying cognitive tests assessed along with change in ADL function, non-motor markers and, if available, biomarker status
- Aim 2.2: Evaluation of progression in IADL function (patient-/informant-ratings) along with change in cognition, non-motor markers and, if available, biomarker status

5. Study duration

Total duration of the study is 2 years.

6. Study population

6.1. Study population

Between March 30th, 2014 and December 31th, 2017, we recruited a large cohort of 268 PD patients within the frame of the "Amyloid-Beta in cerebrospinal fluid as a risk factor for cognitive dysfunction in Parkinson's Disease" (ABC-PD, ethic protocol 686/2013B01) study. Follow-up visits were conducted between July 2018 and September 2020, all patients of the ABC-PD study were contacted for re-examination.

We propose a second follow-up of the already existing longitudinal cohort described above with a longitudinal assessment including neuropsychological in-depth endophenotyping and CSF biomarker analyses. In total 182 patients will be invited to participate in the second

follow-up assessment. If patients are not able to attend a clinical visit in-house, possibility of assessments at patients' homes shall be offered. Moreover, if patients are not able to give consent for study participation (confirmed by an independent physician), the legal guardian will be contacted to give study consent for participation. Legal guardians are defined as persons with legal care directive or lasting power of attorney. For drop-outs different reasons for drop-out will be coded (e.g. deceased, disabled, disinterested/refuse study participation, unable to reach/unknown address).

Diagnosis of cognitive impairment:

Patients were classified as PD-MCI according to Level-II Movement Disorder Society recommendations if cognitive impairment was present but did not significantly interfere with everyday function [25]. PDD was defined according to Movement Disorder Society Task Force criteria [17] if cognitive impairment was present and severe enough to impair ADL function unrelated to motor or autonomic symptoms and at least one behavioral symptom was present to support diagnosis. Cognitive impairment was defined according to Level-I (impairment of global cognition) for patients with minimal assessments, or Level-II (performance below 1.5 standard deviation of the population mean reported in the test manuals on at least two tests) for patients assessed using a full cognitive battery. Patients not meeting either of the diagnostic criteria were classified as PD-CN. Cognitive status at follow-up was defined as the primary study outcome.

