6.3. Recruitment

Participants of the already recruited ABC-PD cross-sectional cohort (ethic protocol: 284/2018BO1) will be asked to participate in the follow-up assessment. Patients who did not agree to participate in a longitudinal study or who have asked not to be contacted after the first cross-sectional assessment will not be contacted again. A drop-out rate of 20% is expected for follow-up retention. Therefore, investigation of 145 patients will be primarily conducted between January 2023 and June 2024. During the executive project phase, around 7 to 9 patients will be assessed per month. Patients will be contacted either via phone or in written form. Reasons for drop-outs will be registered for data analysis.

7. Statistics and Sample size estimation

All following hypotheses will be tested a priori; no post-hoc corrections of p-values will be conducted.

Characterization of study groups: Between-group comparisons at clinical visits will be conducted using Mann-Whitney-U or Welch test (two groups) or Jonckheere-Terpstra test (>2 groups) for numerical variables and χ^2 test or Exact Fisher Test for categorical variables. Post-hoc comparisons for IADL and cognitive variables between groups will be corrected for between-group covariates via linear regression models with group status as dummy coded variable. When follow-up cognitive groups are compared (PD-CN vs. PD-MCI vs. PDD), analyses with covariates will be run twice with reference category set as either PD-CN or PD-MCI.

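### The second follow-up appears limited to the 182 first-follow-up attenders, so 86 of 268 baseline patients (32.1%) have no follow-up, and the completer-based prediction analyses do not address the bias this may cause

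*Combined protocol and SAP*

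**What the plan says.** - **Baseline (Section 3.2).** "Of 268 patients with PD assessed at baseline, 108 (40.3%) had PD-MCI".
- **First follow-up (Sections 3.2 and 6.1).** The approach was to everyone: "all patients of the ABC-PD study were contacted for re-examination". The yield was "182 (61.2%) patients were re-assessed and 164 analysed". The 18 not analysed were 17 patients with deep brain stimulation and one without a cognitive classification.
- **Second follow-up (Section 6.1).** "In total 182 patients will be invited to participate in the second" follow-up assessment. The section does not say in words that these are the first-follow-up attenders.
- **Recruitment (Section 6.3).** "Participants of the already recruited ABC-PD cross-sectional cohort (ethic protocol: 284/2018BO1) will be asked to participate in the follow-up assessment". The only group barred from contact is described as "Patients who did not agree to participate in a longitudinal study or who have asked not to be contacted after the first cross-sectional assessment". "A drop-out rate of 20% is expected for follow-up retention", which leads to 145 patients to be examined.
- **Aim 1.1 (Section 4.1).** "Prediction of conversion rates to PD-MCI (among PD-CN) and PDD (among non-demented patients) according to baseline IADL", together with other baseline markers.
- **Analysis (Section 7).** The Cox models for the predictive value of IADL and cognitive status are limited to patients with all visits completed. Logistic regression and ROC curves with a Youden cut-off follow; both need a follow-up diagnosis. Section 6.3 says reasons for drop-out will be recorded for analysis, but Section 7 does not say how they will be used.

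**The concern.** The questions start at baseline, but the answers come from patients who came back. If the 86 differ from the 182 in their risk of dementia, the results describe returning patients and not the cohort that was profiled.

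What is biased depends on why patients were lost:

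- **Loss depends only on the baseline profile.** Conversion rates within a profile, and hence its predictive values, are preserved. The pooled rate, sensitivity and specificity shift, and the Youden cut-off can shift with them.
- **Loss depends only on the outcome.** Sensitivity, specificity and odds ratios are preserved. Rates and predictive values are not.
- **Loss depends on both.** In general nothing is protected.

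The plan gives no information to tell these cases apart and no analysis to probe them. Events are few: 17 conversions observed by the first follow-up and at most 15 more expected (Section 7). The results are therefore sensitive to who is missing.

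**Working it through.** **1. Who is invited.** Inputs: 182 invited (Section 6.1), 20% drop-out and 145 examined (Section 6.3).

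- 182 × 0.80 = 145.6, which reproduces the stated 145.
- 268 × 0.80 = 214.4 and 164 × 0.80 = 131.2; neither fits.

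The base is 182, the same number as were re-assessed at the first follow-up. The invitation list is evidently the attenders.

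**2. Size of the gap.**

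- 268 − 182 = 86, and 86/268 = 32.1%.
- Retention at the first follow-up is 182/268 = 67.9%. The 61.2% printed beside 182 is 164/268, the analysed fraction.
- If 145 are examined, 145/268 = 54.1% of the baseline cohort reach the second follow-up.

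**3. The observed rate.** 17/164 = 10.4%, as printed. If the 86 had the same risk, 86 × 0.1037 ≈ 9 of their conversions would be unobserved.

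**4. Effect on the pooled first-follow-up rate.** Let k be the risk in the 86 divided by the risk in attenders. The documents do not give k, so all values below are assumptions. The 18 attenders not analysed are taken to have the same risk as the 164.

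Cohort rate = (17/164) × (0.679 + 0.321k)

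Relative understatement = 1 − 1/(0.679 + 0.321k)

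| k (assumed) | 0.679 + 0.321k | Cohort rate | Observed 10.4% is |
|---|---|---|---|
| 0.5 | 0.840 | 8.7% | overstated by 19% |
| 1 | 1.000 | 10.4% | unbiased |
| 1.35 | 1.112 | 11.5% | understated by 10% |
| 2 | 1.321 | 13.7% | understated by 24% |

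Leaving the 18 out, so that the denominator is 164 + 86 = 250, changes little: 8.6% at k = 0.5 and 13.9% at k = 2. The extremes on that denominator are 17/250 = 6.8% if none of the 86 converted and (17 + 86)/250 = 41.2% if all did.

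**5. The recruitment frame.** Section 6.3 names the cross-sectional cohort but attaches ethics number 284/2018BO1. Section 3.2 gives that number to the first follow-up and 686/2013BO1 to the baseline study. Section 6.3 also bars only patients who declined longitudinal participation or further contact, which would be a strange limit if every non-attender were already outside the frame. Sections 6.1 and 6.3 need to be reconciled.

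**The case against.** **The direction is not known.** A reader might infer that the 86 were lost because they declined, so that conversion is certain to be understated. Section 3.1 does link dementia to nursing-home placement and death, and Section 6.1 lists death and disability among its example drop-out codes. But the same list includes refusal and unknown address, and no reasons are reported for the 86. The objection stands: bias is possible, and its sign is open.

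**The 86 were not simply shut out.** All patients were contacted for the first follow-up. Some of the 86 may since have died, refused or become unreachable, so a renewed invitation would recover an unknown part. A patient without a first follow-up visit could not enter a model restricted to completers anyway. This stands, and the remedy therefore does not rest on re-inviting them.

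**Not every analysis is affected.** Odds ratios survive if loss depends on the outcome alone or the predictors alone. The mixed-model paragraph in Section 7 states no completer restriction. Both points stand. It would also be tempting to size the bias by letting patients with both markers (10 of 21 converted) return less often than the rest (7 of 143). That holds the rates within each profile fixed and moves only the pooled rate. Tying it to the 61.2% would also count 18 attenders as lost.

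**Weighting has limits.** Weights built on baseline data cannot correct loss driven by later, unmeasured decline, and the documents do not say that every baseline scale is complete for all 268. This stands and is stated below as a limit. It does not remove the value of seeing whether the results move.

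**The frame conflict may be a labelling slip.** Probably so, since 145 is 80% of 182. It still needs correcting.

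**Conclusion.** The point holds as a possible bias of unknown direction. About a third of the baseline cohort (86/268 = 32.1%) has no follow-up, the reasons are not given, and the prediction analyses rest on those who returned with no planned check on attrition. Baseline-origin conversion rates, predictive values and ROC cut-offs may be understated or overstated.

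The sizes in the table apply to the pooled first-follow-up dementia rate and rest on assumed values of k. They show what would follow from a given difference in risk and do not estimate it. The documents give no basis for a figure on predictive values or cut-offs. This is a recommended improvement to the analysis plan; confidence in the size of any bias is low.

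**What to change.** 1. **Add a weighted sensitivity analysis.** Beside the unweighted results, repeat the baseline-origin conversion, predictive-value and ROC analyses with each assessed patient weighted by the inverse probability of being assessed. Estimate that probability from baseline variables available for the 268, for example age, MoCA, PD-MCI status, FAQ scores, UPDRS-III and disease duration. State how complete these variables are.
2. **Describe the loss.** Tabulate baseline profiles of the 86 against the 182, with reasons for loss where known and deaths shown separately.
3. **Reconcile Sections 6.1 and 6.3.** State whether the frame is the 268 or the 182 and whether any of the 86 will be approached again, and match the cohort name to the ethics number. Correct the percentage printed beside 182 in Section 3.2.

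The cost is some analysis-plan wording and one weighting model on existing data, with no extra visits. Intervals will be slightly wider, and the correction reaches only loss explained by measured baseline variables.

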8.2. Neuropsychological testing

The aim is to diagnose PD-MCI and PDD according to the Level-II recommendations of the Movement Disorder Task Force [17, 18, 25]. Therefore, the following five domains will be quantitatively assessed using the Consortium to Establish a Registry for Alzheimer's Disease (CERAD-Plus) battery, three subtests of the Wechsler Intelligence Test for Adults (WIE), and one subtest of the Leistungsprüfsystem für 50- bis 90-Jährige (LPS 50+). At least two tests are assigned to each cognitive domain:

- Executive functions: Lexical and Phonemic Fluency (CERAD-Plus), Trail Making Test Part B (CERAD-Plus)
- Attention/working memory: Digit-Symbol Test (WIE), Letter-Number Sequencing (WIE)
- Language: Boston Naming Test (CERAD-Plus), Similarities (WIE)
- Memory: Word List Learning, Recall, and Discriminability (CERAD-Plus), Praxis Recall (CERAD-Plus)
- Visuospatial abilities: Praxis (CERAD-Plus), Fragmented Words (LPS-50+)

The MMSE included in the CERAD-Plus, as well as the Montreal Cognitive Assessment (MoCA) will serve as global cognitive screening scales. In addition, the DATE will be applied. The DATE by Johnen and colleagues [29] was developed to assess limb and buccofacial apraxia in neurocognitive disorder patients with Alzheimer's disease and frontotemporal dementia. Based on scores in the first follow-up, progression in the DATE performance over time will be investigated. For validation purpose, the Kölner Apraxie Screening [30] will be included as well. Patients' performance in the DATE and KAS will be videotaped for data analysis. Videotaped data will be solely used for scoring of the DATE and KAS, also including registration of patient's body parts and face. After scoring of patient's test performance and finalization of study analysis, videodata will be deleted. Only, information of patients test performances as a result of the videoanalysis will be shared with collaboration partners.

In addition, we will validate a novel scoring algorithm of patients' cube drawing (CERAD-PLUS test battery) proposed as a measure for retrograde procedural memory [31]. Therefore, investigators will be trained for this novel scoring method by the collaborating group of [name], University of Luxembourg. Patients' performance will be scored by the investigators during test session, therefore, no additional time for patients' examination is expected.

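### Cognitive status is set by two non-equivalent rules, so a change of testing level between visits can look like conversion to PD-MCI, hide a conversion, or look like reversion

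*Combined protocol and SAP*

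**What the plan says.** Section 6.1 states the role of the classification: "Cognitive status at follow-up was defined as the primary study outcome". Impairment is reached by one of two routes. One is "Level-I (impairment of global cognition) for patients with minimal assessments". The other, for patients given the full battery, is "Level-II (performance below 1.5 standard deviation of the population mean reported in the test manuals on at least two tests".

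Earlier in the same paragraph PD-MCI is tied to one route only: "Patients were classified as PD-MCI according to Level-II Movement Disorder Society recommendations if cognitive impairment was present". PDD needs more than the cognitive criterion. ADL function must be impaired for reasons other than motor or autonomic symptoms, and "at least one behavioral symptom was present to support diagnosis".

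For the coming visit, Section 8.2 says: "The aim is to diagnose PD-MCI and PDD according to the Level-II recommendations of the Movement Disorder Task Force". It adds that MMSE and MoCA "will serve as global cognitive screening scales", without a cut-off and without saying what happens if the battery is incomplete.

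Section 7 models conversion by Cox and logistic regression. It limits the Cox analysis to patients who completed all visits, but not to patients classified at the same level each time. It has no adjustment or sensitivity analysis for level.

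**The concern.** Conversion is a difference between two classifications. If one visit is classified on a global score and another on a two-test rule, part of that difference may come from the rule and not from the patient. Each route may be acceptable for a diagnosis at a single visit, but that does not make a difference between routes a conversion.

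Aim 1.1 includes conversion from PD-CN to PD-MCI, where the cognitive criterion decides the category. PD-CN versus PD-MCI is also a predictor in the Cox models, so the level used at an earlier visit affects the exposure as well as the outcome. If the level a patient receives is related to IADL ratings, the resulting errors would be differential and could bias the IADL-conversion association upwards or downwards.

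**Working it through.** **The plan's nearest figures.** The plan gives no figure for the effect of mixing levels. Its expected sample is reproduced: 182 x 0.80 = 145.6, stated as 145. Its maximum of 15 further PDD converters agrees with 145 x 17/164 = 15.03, although Section 7 does not show that derivation.

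**Inputs**
- Level-II rule: at least two tests below -1.5 SD (Section 6.1).
- Number of tests: Section 8.2 assigns at least two to each of five domains, so 5 x 2 = 10 is the minimum. Counting every listed score separately gives 3 + 2 + 2 + 4 + 2 = 13.
- Level-I scale and cut-off: not given. Assumed here to be one normally distributed score with a cut-off of -1.0, -1.5 or -2.0 SD.
- Share of patients at Level-I, and share changing level: not given.

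**Step 1: are the rules equivalent at normal cognition?** The chance that one test falls below -1.5 SD is p = 0.0668. For k independent tests, P(at least 2 below) = 1 - (1 - p)^k - k p (1 - p)^(k-1).
- k = 10: 14.1%
- k = 13: 21.4%
- one score below -1.5 SD: 6.7%

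Independence is a simplification. With between-test correlations of 0.3 to 0.7, simulation gives 13.8% to 21.2% for the Level-II rule, so the gap remains.

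**Step 2: which way do the rules disagree?** I simulated 200,000 patients per setting. One latent ability drives all tests and accounts for 70% of the variance of the global score. Mean shifts ran from 0 to -1.5 SD. Everything except the Level-II rule is an assumption. Two settings with ten tests, as a share of all simulated patients:

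| Mean shift, test correlation | Level-I cut-off | Impaired by Level-I only | Impaired by Level-II only |
|---|---|---|---|
| 0, 0.7 | -1.0 SD | 6.9% | 4.9% |
| 0, 0.7 | -1.5 SD | 1.6% | 8.8% |
| 0, 0.7 | -2.0 SD | 0.2% | 11.8% |
| -1.0 SD, 0.5 | -1.0 SD | 6.7% | 17.1% |
| -1.0 SD, 0.5 | -1.5 SD | 1.9% | 31.6% |
| -1.0 SD, 0.5 | -2.0 SD | 0.3% | 45.0% |

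Across all settings, 0-9% are impaired by Level-I only and 5-62% by Level-II only. On a move from Level-II to Level-I, the first group would look like new impairment, and the second would look unimpaired (a missed conversion or an apparent reversion). On the opposite move the roles swap. Level-I-only exceeds Level-II-only just in some settings with the lenient -1.0 SD cut-off. The balance therefore turns on a number the plan does not state.

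**Step 3: scale, for illustration only.** Suppose 5-20% of 145 patients change level and 5-30% of those change class on the cognitive criterion.
- Low: 145 x 0.05 x 0.05 = 0.4 patients.
- High: 145 x 0.20 x 0.30 = 8.7 patients.

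These are changes in either direction on the cognitive criterion. They should not be divided by the 15 expected converters, who are PDD cases.

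**Step 4: which outcomes are exposed?** For PD-CN versus PD-MCI the cognitive criterion is decisive, provided Level-I is accepted for PD-MCI despite the Level-II sentence. For PDD, a change of level matters only in patients who also meet the ADL and behavioural criteria.

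**The case against.** The strongest reply is that the planned testing at this follow-up is Level-II. The classification paragraph is in the past tense, Section 8.2 sets Level-II as the aim with at least two tests per domain, and Table 1 counts the battery as mandatory. Home visits are not described as shortened. Few patients, or none, may be classified at Level-I. That stands as a limit on size. It does not close the point: earlier visits feed the same conversion variable, Section 8.1 brings in routine-care and other-study data, and the plan has no rule for an incomplete battery.

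A second reply is that the main hypothesis concerns PD-MCI to PDD. PD-MCI patients already meet the cognitive criterion, and a change of level alone cannot produce PDD. This is right, and it confines the direct exposure mainly to the PD-CN to PD-MCI part of Aim 1.1. Aims 1.2 and 2.1 use cognitive scales or tests rather than the category.

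A reader might also infer that false conversions cluster in the frailest patients and inflate the IADL association. The documents do not support this. They do not say who had minimal assessments or why, or that this grows more common over time. The 115-minute mandatory session, home visits and guardian consent make a link with frailty plausible, but it remains an inference. A move to Level-I may also hide conversions more often than it creates them, which in patients with poor IADL would weaken the association.

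**Conclusion.** The point holds in a limited form. The primary outcome rests on two rules that flag different patients, the plan does not say how a change of level between visits is handled, and no analysis protects the conversion results from it. Two statements in Section 6.1 also need to be reconciled: PD-MCI by Level-II, and impairment by either level.

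The size cannot be computed, because neither the number at each level nor the Level-I cut-off is given. The illustrative 0.4 to 8.7 patients rests wholly on assumed shares. The non-equivalence is firmer: 14.1-21.4% against 6.7% at normal cognition, assuming independent tests and a Level-I cut-off of -1.5 SD.

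A reader might be tempted to multiply the patients tested at Level-I by an assumed Level-I false-positive rate and call the result artefactual conversions. That overcounts, because Level-II has false positives too; only disagreement between the rules is caused by the change of level. This is a modest point, worth acting on because the remedy is cheap.

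**What to change.** 1. Reconcile the Level-I and Level-II sentences in Section 6.1. State whether Level-I can establish PD-MCI, which global scale and cut-off define it, and what applies when the battery is incomplete.
2. Record the level used for each patient at each visit and report a cross-tabulation of level by visit.
3. Repeat the Cox and logistic conversion models of Section 7 in patients classified at Level-II at every visit.
4. Optionally, add a version that applies one Level-I global-score rule to all patients at all visits where the score was recorded.

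Earlier status should not be re-derived only in patients who are later tested at Level-I. Earlier cognitive status is a predictor in the Cox models, and that step would define it from post-baseline information.

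The cost is a written rule, one recorded variable and one repeated analysis, with no added patient burden. The same-level analysis has fewer patients and may select less impaired ones, so it belongs beside the main analysis as a sensitivity analysis and should not replace it.
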